1.1. Study Objective

To evaluate the safety and efficacy of the scoring balloon catheter manufactured by Sino Medical Sciences Technology Inc. for the treatment of coronary artery stenotic lesions.

1.2. Indications

Scoring balloon catheter are employed to treat coronary artery stenosis, including in-stent restenosis and complex C-type lesions, thereby improving myocardial perfusion.

1.3. Study Design

This prospective, multicentre, randomised, parallel-group, non-inferiority trial design evaluated the safety and efficacy of the scoring balloon catheter. The trial planned to enrol 136 patients with coronary artery stenotic lesions. Following the signing of informed consent forms, all subjects underwent coronary angiography after investigators determined compliance with patient-related inclusion criteria and absence of patient-related exclusion criteria. If the angiographic findings met the inclusion criteria and excluded the exclusion criteria, subjects were randomly assigned to either the trial group or the control group (with a 50% probability of allocation to each group) for balloon dilatation of the lesion. Subjects in the trial group received balloon dilatation using the scoring balloon catheter developed by Sino Medical Sciences Technology Inc. Subjects in the control group received balloon dilatation using the NSE Coronary Dilatation Catheter (National Medical Device Import Registration No. 20163035067) developed by Goldman Co., Ltd.

Follow-up time points during this trial included pre-PCI, intra-procedural, and post-procedural follow-up until discharge. The primary endpoint was device success rate (by lesion level), with secondary endpoints comprising procedural success rate (by patient level). Concurrent safety endpoints comprised the composite target lesion failure (TLF) rate from procedure initiation to discharge and its constituent events, patient-oriented composite endpoints (PoCE) and its constituent event rates, alongside other procedure-related adverse events and serious adverse events (e.g., balloon rupture, vascular dissection, in-stent thrombosis), and device deficiency.

1.4. Trial flowchart

Item Timepoint	Screening Period	Treatment Period	Follow-up Period
	Preoperative (D-14 to D-0)	Surgical Procedure (D 0)	Postoperative to Pre- Discharge
Signing of informed consent form	▲		
Demographic Data	▲		
Medical history	▲		
Vital Signs ¹	▲	▲	▲
Pregnancy Test ²	▲		
Complete Blood Count, Blood Biochemistry ³	▲		▲
Cardiac Enzyme Panel ⁴	▲		▲ (within 48 hours post-procedure)
Electrocardiogram ⁵	▲		▲ (Within 48 hours post-procedure)
Inclusion/Exclusion Criteria	▲		
Centralised randomisation	▲		
Clinical Evaluation		▲	
Coronary angiography ⁶		▲	
Coagulation Function ⁷	▲		
Cardiovascular adverse events ⁸		▲	▲
Adverse events and serious adverse events		▲	▲
Device deficiency		▲	
Cardiovascular concomitant medications	▲	▲	▲

Notes:
 1) Vital signs: systolic blood pressure, diastolic blood pressure, and heart rate.
 2) Pregnancy test: Applicable only to women of childbearing age.
 3) To safeguard the rights of trial participants, blood count and biochemical test results obtained within one month prior to operative shall be accepted (where multiple tests exist, the most recent result shall prevail): □ Blood count: White blood cell count (WBC), red blood cell count (RBC), platelet count (PLT), haemoglobin (HB); □ Renal function: Serum creatinine (SCr); □ Liver function: Alanine aminotransferase (ALT), Aspartate aminotransferase (AST); ④ Lipid profile: Triglycerides (TG), Total cholesterol (TC), High-density lipoprotein cholesterol (HDL-C), Low-density lipoprotein cholesterol (LDL-C).
 4) Cardiac enzyme panel: Creatine kinase (CK), Creatine kinase MB isoenzyme (CK-MB), Cardiac troponin T (cTnT)/Cardiac troponin I (cTnI) (either one may be selected; both are not required). Note: Postoperative cardiac enzyme panel should be completed within 48 hours post-procedure. Should results be abnormal and clinically significant, repeat testing is required prior to discharge.
 5) Postprocedure electrocardiogram (ECG) should be performed within 48 hours postprocedurally.
 6) Coronary angiography shall be performed immediately postprocedurally at each centre and recorded onto optical disc.

Item Timepoint	Screening Period	Treatment Period	Follow-up Period
	Preoperative (D-14 to D-0)	Surgical Procedure (D 0)	Postoperative to Pre-Discharge
7)	Coagulation function includes prothrombin time (PT), activated partial thromboplastin time (APTT), thrombin time (TT), and fibrinogen (FIB). To safeguard subject rights, results from tests conducted within one month prior to procedure will be accepted.		
8)	Cardiovascular adverse events comprise major adverse cardiac events (MACE: including all-cause mortality, myocardial infarction [MI], and target lesion revascularisation [TLR]), target lesion failure (TLF, comprising cardiac death, target vessel myocardial infarction [TV-MI], and clinically-indicated target lesion revascularisation [CI-TLR]), and patient-oriented composite endpoints (PoCE, encompassing all-cause mortality, all myocardial infarctions, and all revascularisation events [target lesion revascularisation (TLR), target vessel non-target lesion revascularisation [TVR], and non-target vessel revascularisation).		

Figure1 Trial flow chart

1.5. Sample size

Based on literature review, clinical experience, and results from studies evaluating scoring balloon catheters for coronary artery disease, it is hypothesised that the study group's Sino scoring balloon dilation catheter will demonstrate comparable efficacy to the control group's Goodman coronary NSE balloon catheter, with an anticipated device success rate of 96%. Considering factors such as operator skill variation, lesion complexity, and subject comorbidities and disease severity, the sponsor, clinical experts, investigators, and statisticians jointly determined a non-inferiority margin Δ of -10%, a one-sided test α of 0.025, and a test power (1- β) of 0.8. PASS software calculations yielded a total sample size of 122 subjects, with 61 subjects in each group. Accounting for a 10% dropout rate, the trial requires 136 subjects, distributed as 68 in each group. The sample size calculation formula is as follows:

$$n_T = n_C = \frac{\left(Z_{1-\frac{\alpha}{2}} + Z_{1-\beta}\right)^2 [P_C(1 - P_C) + P_T(1 - P_T)]}{(|D| - \Delta)^2}$$

Where n_T and n_C denote the sample sizes for the treatment and control groups respectively, $Z_{1-\frac{\alpha}{2}}$ and $Z_{1-\beta}$ represent the quantiles of the standard normal distribution, P_T and P_C denote the expected event rates for the treatment and control groups respectively, $|D| = |P_T - P_C|$ denotes the absolute difference in expected rates between the two groups, and Δ denotes the non-inferiority margin, taken as a negative value.

This trial will be conducted concurrently across multiple clinical trial sites. In principle, enrolment numbers will be distributed as evenly as possible among centres to ensure adequate representativeness. However, considering feasibility and enrolment progress, adjustments to enrolment quotas for participating sites will be made based on actual circumstances, striving to maintain balanced enrolment scales across centres. The final enrolment size for any single centre shall not exceed 50% of the total number of cases.

2. Evaluation Criteria

2.1. Efficacy Evaluation

2.1.1. Primary efficacy endpoint

The primary efficacy endpoint of this clinical trial is the device procedural success rate (by lesion level).

Device usage success (by lesion level) requires simultaneous fulfilment of the following conditions:

- a. The balloon must successfully complete the entire balloon dilatation procedure, including delivery, passage through the lesion, inflation, deflation, and withdrawal;
- b. Immediate post-PCI residual stenosis at the target lesion $\leq 30\%$ (post-PCI residual stenosis for ISR and drug-coated balloon restenosis lesions $< 50\%$).

2.1.2. Secondary efficacy endpoint

The secondary efficacy endpoint of this clinical trial is procedural success rate (by subject level).

Achieving procedural success (by the subject level) requires simultaneous fulfilment of the following conditions:

- a. At least one target lesion demonstrates immediate post-PCI residual stenosis $\leq 30\%$ (for ISR and drug-eluting balloon restenosis lesions, residual stenosis $< 50\%$);
- b. Absence of major adverse cardiac events (MACE) during the postprocedure hospital stay: all-cause mortality, myocardial infarction (MI), and target lesion revascularisation (TLR).

2.2. Safety Evaluation

1) Target lesion failure composite endpoint (TLF) incidence

Any of the following events constituted a TLF:

- a. Cardiovascular death (including cases where the cause of death is uncertain but considered cardiovascular in origin);
- b. Target Vessel-Related Myocardial Infarction (TV-MI);
- c. Clinically-indicated target lesion revascularisation (CI-TLR).

Evaluation method: The observation period spans from the commencement of procedure until discharge. For each subject, the incidence rates of individual events and the composite event rate are calculated.

2) Incidence of the patient-oriented composite endpoint (PoCE)

Any occurrence of the following events constituted a PoCE:

- a. All-cause mortality;
- b. All myocardial infarctions;
- c. All recurrent revascularisation events, including target lesion revascularisation (TLR), target vessel non-target lesion revascularisation (TVR), and non-target vessel revascularisation.

Evaluation method: The observation period spans from the commencement of procedure until discharge. For each subject, the incidence rate of individual events and the composite event rate shall be separately calculated.

3) Incidence of Individual Adverse Events and Serious Adverse Events

Evaluation Method: The observation period spans from the commencement of procedure until discharge. Other potential adverse events include balloon rupture, vascular perforation, dissection, acute occlusion, vasospasm, thrombosis (including in-stent thrombosis), and arrhythmias requiring intervention. The incidence rate of each individual event shall be separately calculated.

4) Incidence of device deficiency

3. Analysis Data Set

Full Analysis Set (FAS): The population defined according to the intention-to-treat principle, comprising all subjects who were randomised and received the study product. For patients with missing primary efficacy endpoint data, worst observation carried forward (WOCF) was applied.

Per-protocol set (PPS): Subgroup of the completed trial population excluding major protocol deviations (e.g., subjects breaching inclusion or exclusion criteria).

Safety Set (SS): Refers to the dataset comprising subjects who used the investigational device and for whom safety endpoints were recorded.

Efficacy analyses will be conducted based on both the full analysis set and the per-protocol set. All baseline demographic analyses utilise data from the full analysis set, while safety evaluations employ the safety set.

4. Handling of missing data

For patients in the FAS who did not have an observation for the primary efficacy endpoint, worst observation carried forward was applied. For target lesions where device success could not be determined, imputation was performed as 'device failure'. No imputation was performed for secondary endpoints or efficacy endpoint in the PPS. Missing safety data were not imputed.

5. Statistical Analysis Methods

5.1. General Principles

Data description and analysis were performed using SAS software. All statistical tests employed two-sided significance testing (unless otherwise specified). Confidence intervals were calculated at the 95% confidence level.

1) Statistical Description: Quantitative indicators were described by calculating mean, standard deviation, median, minimum, maximum, lower quartile (Q1), and upper quartile (Q3). Categorical indicators were described by number and percentage of cases in each category. Grading indicators were described by number and percentage of cases in each grade.

2) Statistical inference: Comparisons between two groups will employ appropriate methods based on the nature of the indicator. For quantitative indicators, inter-group comparisons will utilise paired t-tests (assuming equal variance and normal distribution) or Wilcoxon signed-rank tests, depending on data distribution. Categorical indicators will be analysed using chi-square tests or exact probability methods (where chi-square is inappropriate). Ordinal data will be assessed via Wilcoxon signed-rank tests or the Mann-Whitney U test.

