### 6.1.2 Allocation of Sample Size

The inclusion/exclusion criteria for the selected subjects are strictly restricted in this trial protocol, and all selected 136 subjects are diagnosed with coronary artery stenosis (including in situ or restenotic lesions). The subjects screened are randomized at 1:1 to receive the investigational medical device or the control device for treatment, and the device success rate is set as the primary endpoint.

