## 6.4.2 Statistical Analysis Methods

### (1) General Principles for Statistical Analysis

In this study, SAS software is used for data description and analysis. All statistical tests are conducted by two-sided test (unless otherwise specified). The 95% confidence is adopted for the confidence interval (CI). In addition to the statistical methods listed below, detailed and additional exploratory analyses may be required and confirmed in the Study Reports and Statistical Analysis Plan (SAP).

- 1) Statistical description: For the description of quantitative indicators, the mean, standard deviation (SD), median, minimum, maximum, lower quartile (Q1) and upper quartile (Q3) will be calculated; for the categorical indicators, the number of cases and percentage for each category will be described.
- 2) Statistical inference: The inter-group comparison in general condition will be conducted by using appropriate method according to the types of indicators. The inter-group comparison in quantitative data will be conducted by the group t-test (homogeneity of variance and normal distribution) or Wilcoxon rank sum test according to the data distribution. The categorical data will be analyzed by the Chi-squared Test or Exact Test (if the Chi-squared Test is not applicable), while the ranked data will be analyzed by the Wilcoxon rank sum test or CMH test.

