5.4. Efficacy Analysis

5.4.1. Primary Efficacy Endpoints

Primary efficacy evaluation is based on the Full Analysis Set (FAS) and the Per-Protocol Set (PPS).

This trial employs a multicentre, randomised, parallel-group, non-inferiority design. The primary efficacy endpoint is device procedural success rate (by lesion level), with the following hypothesis testing:

$$H_0 : p_T - p_C \leq -\Delta$$

$$H_1 : p_T - p_C > -\Delta$$

In the formula, $p_{(T)}$ denotes the device usage success rate for the experimental group, p_C represents the device usage success rate for the control group, and $-\Delta$ signifies the non-inferiority margin, set at -10%.

At $\alpha=0.025$ (one-sided test) and $\beta=0.2$, the device procedural success rate (by lesion level) of the experimental group is compared with that of the control group. The difference in device procedural success rates (by lesion level) between the two groups is calculated, along with the 95% confidence interval for this difference. Based on the lower limit of the confidence interval, a judgement is made as to whether the non-inferiority criterion has been met. If the lower limit of the 95% confidence interval is not less than -10%, the conclusion of non-inferiority is established. Should centre effects require consideration, the CMH chi-square test shall be employed.

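### SAP 5.1 names paired-sample tests for quantitative comparisons between two independent arms, contrary to Protocol 6.4.2; the primary, secondary and composite safety analyses are not affected

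*SAP*

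**What the plan says.** SAP 5.1 (General Principles, item 2) covers comparisons between the two groups. For quantitative indicators it says that "inter-group comparisons will utilise paired t-tests (assuming equal variance and normal distribution) or Wilcoxon signed-rank tests, depending on data distribution". For ordinal indicators: "Ordinal data will be assessed via Wilcoxon signed-rank tests or the Mann-Whitney U test". Categorical indicators go to chi-square or exact methods.

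Protocol 6.4.2 (1) covers the same ground with different tests: "The inter-group comparison in quantitative data will be conducted by the group t-test (homogeneity of variance and normal distribution) or Wilcoxon rank sum test", chosen according to the data distribution. For ordinal data, "the ranked data will be analyzed by the Wilcoxon rank sum test or CMH test".

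On the design, SAP 5.4.1 says: "This trial employs a multicentre, randomised, parallel-group, non-inferiority design". Protocol 6.1.2 says: "The subjects screened are randomized at 1:1 to receive the investigational medical device or the control device for treatment". Neither document describes matching of subjects, lesions or devices across arms.

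Protocol 6.4.7 says that the main methods should in principle not be changed and that any modification is to be recorded. The SAP text available gives no reason for a change of test.

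**The concern.** A paired t-test or a signed-rank test works on within-pair differences. It needs a rule that links each test-arm observation to one control-arm observation. No such link exists in a parallel-group trial, so both tests named for quantitative data are the wrong kind, and SAP 5.1 offers no valid alternative for that data type. For ordinal data one of the two listed options is valid and one is not, with no rule for choosing.

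At stake are the between-arm p-values for continuous variables:

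- **Baseline:** age, weight, height and BMI (Table 4), ejection fraction (Table 5), vital signs (Table 6).
- **Lesion and device use:** lesion length, vessel diameter and stenosis (Table 12); diameters, lengths, pressures and times (Tables 13-17).
- **Angiographic results:** percent residual stenosis (Table 21, continuous rows) and QCA (Tables 54-56).

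A statistician following the SAP to the letter would either be unable to produce these p-values or would report values with no defined meaning.

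**Working it through.** **1. Tests side by side**

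| Data type | Protocol 6.4.2 | SAP 5.1 | Valid for independent arms? |
|---|---|---|---|
| Quantitative | Group t-test or rank sum | Paired t-test or signed-rank | Protocol yes; SAP no |
| Ordinal | Rank sum or CMH | Signed-rank or Mann-Whitney U | Protocol yes; SAP only Mann-Whitney U |
| Categorical | Chi-square or exact | Chi-square or exact | Both yes |

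The SAP sentence cannot be read as a pre/post comparison. It refers to comparisons between groups, and SAP 5.5 handles pre/post laboratory results by cross-tabulation.

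**2. The plan's own figure.** The sample size (SAP 1.5, Protocol 6.1.1) uses 96% success in both arms, a margin of -10%, one-sided alpha 0.025 and power 0.8:

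n per arm = 7.85 × (0.96×0.04 + 0.96×0.04) / 0.10² = 60.3, rounded up to 61. With 10% dropout, 61/0.9 = 67.8, rounded up to 68 per arm, 136 in total.

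This reproduces the plan. It rests on a binary endpoint, so the tests in dispute do not enter it.

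**3. Can the paired tests be run?** They need equal counts in the two arms.

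- A trial run with 68 and 66 observations failed: the paired test is undefined.
- Up to two lesions per subject are allowed (Protocol 5.2.1, item 6), and Tables 12 and 21 are by lesion. Most measures in Tables 13-17 are by device.
- Table 21 divides lesions into de novo, in-stent restenosis and drug-balloon restenosis, with numbers per arm left to chance. The PPS removes further subjects.

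The documents give no proportion q of subjects with two lesions, so q is assumed here. With exactly 68 subjects per arm, the chance of equal lesion totals is the sum over k of [Bin(k; 68, q)]²:

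| Assumed q | P(equal lesion counts) |
|---|---|
| 5% | 16% |
| 10% | 11% |
| 30% | 7% |

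**4. What happens when counts are equal?** With n per arm, means a and b, variances sₐ² and s_b², and sample covariance c under the chosen row order:

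- Two-sample t = (a − b) / √[(sₐ² + s_b²)/n], with 68 + 68 − 2 = 134 degrees of freedom (critical value 1.978).
- Paired t = (a − b) / √[(sₐ² + s_b² − 2c)/n], with 68 − 1 = 67 degrees of freedom (critical value 1.996).

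The numerators are identical. The statistics differ only through c, which reflects row order and averages zero over arbitrary pairings. The paired p-value is therefore arbitrary in a single data set but almost correct in the long run.

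Simulation: normal data, SD 1, 68 independent observations per arm, two-sided 5% level; 10,000 data sets for the t-tests and 3,000 for the rank tests.

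| | Paired t | Two-sample t | Signed-rank | Mann-Whitney U |
|---|---|---|---|---|
| Type I error | 0.054 | 0.052 | 0.053 | 0.050 |
| Power at 0.5 SD (assumed) | 0.822 | 0.827 | 0.815 | 0.815 |

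The simulation standard error of the type I rates is √(0.05×0.95/10,000) = 0.002 for the t-tests and √(0.05×0.95/3,000) = 0.004 for the rank tests.

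In one data set with an assumed true difference of 0.4 SD, the two-sample t-test gave p = 0.012. Over 2,000 arbitrary pairings of the same numbers the paired p ran from 0.001 to 0.034, with a central 95% of 0.005 to 0.026.

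**5. Which analyses do not use these tests?**

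- Primary endpoint: binary, judged by the lower limit of the 95% CI for the rate difference (SAP 5.4.1).
- Procedural success: categorical (SAP 5.4.2).
- TLF and the subject-level composite: categorical; adverse events and device deficiencies: incidence rates (SAP 5.5).
- Table 21 rows for meeting the 30% or 50% threshold: yes/no, hence categorical.

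**The case against.** The strongest reply is that this is a slip of language. The equal-variance condition attached to the paired t-test belongs to the two-sample test, and the sentence otherwise follows the protocol's. Other SAP terms also look mistranslated, such as the mammary balloon in Table 17. An experienced programmer would run the correct tests, and unequal counts would expose the error. This is persuasive about intent, but the documents do not confirm it, and the SAP text as written is still wrong.

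Three stronger readings are tempting and should be resisted:

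- A reader might infer that every ordinal comparison is invalid too. SAP 5.1 also permits the Mann-Whitney U test, so a valid route exists.
- A reader might infer an inflated false-positive rate. With equal counts and arbitrary pairing, error rates and power barely move.
- A reader might infer that the non-inferiority conclusion is at risk because residual stenosis is part of device success. Only the threshold result enters the endpoint, and it is analysed as categorical.

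Table 57 (acute lumen gain) and Tables 52-53 (vital signs) appear as titles only. No p-value row is shown, so they are not counted as affected.

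**Conclusion.** The point stands in limited form. SAP 5.1 names the wrong class of test for all quantitative between-arm comparisons and one unsuitable option for ordinal ones, and it contradicts Protocol 6.4.2. The consequence is a supportive p-value that is undefined (unequal counts) or arbitrary (equal counts), not a biased trial result. The size of the row-order effect comes from simulated normal data with assumed differences and one observation per subject; the chance of equal lesion counts rests on an assumed 5-30% of subjects with two lesions. That the tests are wrong in kind rests on neither assumption. This should be corrected, but it is not a condition for the trial's conclusion to be valid.

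**What to change.** In SAP 5.1, item 2:

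- Quantitative indicators: replace the paired t-test with the independent two-sample t-test, and the Wilcoxon signed-rank test with the Wilcoxon rank-sum (Mann-Whitney U) test.
- Ordinal indicators: delete the signed-rank option and use the rank-sum or CMH test, as in Protocol 6.4.2.

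Record the correction as Protocol 6.4.7 requires, before database lock. The cost is one edited passage. Sample size, data collection, endpoints and the protocol stay as they are.
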